NUMBER OF SUBJECTS PLANNED AND DURATION OF PARTICIPATION:	Approximately 60 subjects will participate in this study. The total duration of participation may include up to 10 days of screening and up to nine (9) days of treatment. Subjects may have up to an additional 30 days of follow-up for safety for treatment-related adverse events that have not resolved by the final follow-up visit on Day 6-9.
NUMBER OF STUDY SITES:	This will be a multi-center study conducted at approximately 15 study sites.
INCLUSION CRITERIA:	
The Subject:
 
 
1. is anticipated to be hospitalized for the duration of treatment (minimum of 6 days).
 
2. is <math>\geq</math> 18 years of age.
 
3. or their legally authorized representative is able to provide informed consent.
 
4. has been diagnosed with a wound (chronic, acute, traumatic, or dehisced wounds) and/or ulcer (ie, full-thickness wounds) that meets the following criteria: 
 
a) total surface area measuring <math>\geq 16 \text{ cm}^2</math>, including a minimum width of 2 cm (before removal of eschar at the bedside and excluding undermining).
 
b) <math>< 20 \text{ cm}</math> across (edge-to-edge) at any point perpendicular to the wound edges.
 
 
 
5. has, in the opinion of the investigator, no more than 2/3 of the wound bed surface area considered to be clean, healthy, and viable. If eschar is present at baseline, it must be removed by bedside debridement prior to assessing the percentage of clean, healthy, viable wound bed.
 
6. has a negative urine or serum pregnancy test at screening (if female and has potential for pregnancy) and is willing to take precautionary measures to prevent pregnancy during the duration of the study (up to 9 days).
 

EXCLUSION CRITERIA:	
The Subject:
 
 
1. has been diagnosed with a malignancy in the wound.
 
2. has untreated osteomyelitis.
 
3. has an untreated systemic infection.
 

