### **3.1.3. Duration of Study Participation**

The duration of study participation for each Subject is as follows:

- Screening Period: up to 10 days (Day -10 to Day 0)
- Treatment Period: up to nine (9) days (Day 0 to Day 9)

The maximum participation duration per Subject is up to 19 days.

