## 4.4. Subject Withdrawal or Termination

### 4.4.1. *Reasons for Withdrawal or Termination*

Subjects may withdraw from participation in the study at any time upon request.

The Investigator may choose to terminate the participation of a Subject from the study with or without their consent for any of the following reasons:

- Adverse events
- Noncompliance
- For any reason that may, in the opinion of the Investigator, negatively affect the safety or well-being of the Subject

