### 4.4.2. *Handling of Withdrawal or Termination*

Every effort should be made to complete wound and AE assessments prior to the Subject withdrawal.

For Subjects who are lost to follow-up, the Investigator will make attempts to collect at least the vital status (eg, whether the Subject is alive) before formally withdrawing the Subject from the study. Prior to considering a Subject lost to follow-up, at least two documented attempts should be made to contact the Subject through all available routes, and a certified letter should be sent to the permanent address on file.

Once the Subject withdraws from the study, no further study evaluations will be performed, and no additional data will be collected. The Investigator may retain and continue to use any data collected before withdrawal. The Subject will not be replaced.

If, for any reason, the Subject is withdrawn by the Investigator from this study, the Investigator will inform the Subject and KCI™.

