## **7.7. Follow-up Period for Ongoing AEs**

Treatment-related AEs (serious and non-serious) that are ongoing at the final study visit will be followed up to 30 days to assess resolution or stabilization. All unrelated AEs will be considered closed at the time the Subject completes participation in the study.

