9.2. Adverse Events

All treatment-emergent adverse events (TEAEs), which are defined as adverse events with onset or worsening of pre-existing conditions on or after the initial dressing application through the course of the study, will be summarized. The number and percentage of treated Subjects who experienced at least one adverse event in each system organ class by preferred term will be summarized. In any given category (e.g., system organ class or preferred term), a Subject will be counted only once. The denominator for the calculation of percentages will be the number of Subjects in the Safety analysis set. The test for significant between-treatment differences will be carried out using the Fisher's exact test.

The following summary tables and listings will be presented by treatment arm:

- Overview of all treatment-emergent adverse events (TEAEs)
- Incidence of all treatment-emergent adverse events (TEAEs) by system organ class and preferred term
- Incidence of all treatment-emergent adverse events (TEAEs) by system organ class, preferred term, and maximum severity
- Incidence of all serious adverse events (SAEs) by system organ class and preferred term
- Incidence of treatment-related TEAEs by system organ class and preferred term
- Incidence of treatment-related TEAEs by system organ class, preferred term, and maximum severity
- Incidence of treatment-related serious adverse events (SAEs) by system organ class and preferred term
- Incidence of most common >5% TEAEs in any one treatment group by preferred term only
- Listing of all treatment-related adverse events
- Listing of all treatment-related serious adverse events (SAEs)
- Listing of discontinuations: Subjects who discontinued from the study due to any adverse event
- Listing of deaths: Subjects who died of any cause during the study

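### Protocol 4.4.2 and 7.7 are not reconciled, so a subject terminated by the investigator for a treatment-related adverse event can lose that event's outcome

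*Protocol*

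**What the plan says.** **Leaving the study.** Protocol 4.4.2 has a heading that covers both withdrawal and termination, and it gives one data rule: "Once the Subject withdraws from the study, no further study evaluations will be performed, and no additional data will be collected". The section opens with a request for assessment at exit: "Every effort should be made to complete wound and AE assessments prior to the Subject withdrawal". After the data rule it describes removal by the investigator with the same verb: "If, for any reason, the Subject is withdrawn by the Investigator from this study, the Investigator will inform the Subject". Section 4.4.1 lets the investigator "terminate the participation of a Subject from the study with or without their consent", and adverse events come first in the list of reasons.

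**Follow-up of open events.** Protocol 7.7 says that treatment-related events, serious or not, "that are ongoing at the final study visit will be followed up to 30 days to assess resolution or stabilization". Unrelated events are closed when the subject completes participation. The synopsis is softer: "Subjects may have up to an additional 30 days of follow-up for safety for treatment-related adverse events", limited to events unresolved at the last follow-up visit, which it places at Day 6-9. SAP 3.1 repeats the synopsis.

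**What the safety data should contain.** Section 7.4 asks for the outcome of every adverse event and for a flag if the event ended participation. The schedule in 5.1 (footnote 6) and section 5.2.5 provide an end-of-study record for a subject withdrawn early. Section 5.2.5 includes adverse event assessment and serious event reporting at that visit. SAP 9.2 tabulates events by maximum severity and by seriousness, and it includes this item: "Listing of deaths: Subjects who died of any cause during the study".

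**The concern.** A subject whose related adverse event is bad enough for the investigator to end participation is one whose later course matters for safety. Read literally, 4.4.2 stops recording for that subject at exit. A subject with the same event who stays to Day 6-9 is followed under 7.7. Two sites can therefore handle the same event differently, each with a protocol section to point to.

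The data at stake are the event's outcome, any later rise in severity or seriousness, and any new event or death in the remainder of the planned treatment window. The sponsor's evaluation of unanticipated device effects in 7.6 works from the serious events it receives, so a worsening that is not collected would not reach it. The trial is open-label and termination is the investigator's decision, so the loss could differ by arm. The documents do not show whether it would, or in which direction.

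**Working it through.** There is no statistical figure to reproduce. The check is a reading of the passages against each other, with a little arithmetic.

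**1. Does the stop in 4.4.2 reach a subject terminated by the investigator?** The sentence speaks of the subject withdrawing, and 4.4.1 uses *withdraw* for the subject's own act and *terminate* for the investigator's. Against that, the heading of 4.4.2 covers both, the section itself speaks of withdrawal by the investigator, and no other data rule exists for terminated subjects. Both readings are possible. The wider one fits the heading better.

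**2. Which visit is the final one in 7.7?** It is either the early end-of-study visit of 5.1 footnote 6 and 5.2.5, or the Day 6-9 visit named in the synopsis and SAP 3.1.

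**3. Combining the readings** for a subject terminated with a related event still open:

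| Stop in 4.4.2 | Final visit in 7.7 | Result |
|---|---|---|
| covers termination | early end-of-study visit | 4.4.2 gives 0 days and 7.7 gives up to 30: direct conflict |
| covers termination | Day 6-9 only | no follow-up: the subject falls outside 7.7 |
| voluntary only | Day 6-9 only | no rule for this subject in either section |
| voluntary only | early end-of-study visit | 7.7 applies, up to 30 days |

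Only the last combination preserves the event's outcome, and nothing in the documents selects it.

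**4. What is kept and what can be lost.**
- Kept: the event itself. It began before exit, so it counts in subject incidence, which is the safety endpoint (Protocol 3.5, SAP 4.2). Its status at exit and the discontinuation flag are also kept.
- At risk: its outcome after exit, a later upgrade in severity or seriousness, and new events or death between exit and the planned Day 6-9 date.

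**5. Durations.** Screening of 10 days plus treatment of 9 days gives 10 + 9 = 19 days, the figure in 3.1.3. With the additional follow-up the span is 19 + 30 = 49 days for a subject with an unresolved related event.

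**6. Size.** Neither document gives an expected number of terminations for adverse events, so no effect can be estimated. A conditional figure is available. Assuming all of about 30 randomized subjects per arm are treated, one new or upgraded event that goes unrecorded after exit changes that arm's incidence of that category by 1/30 = 3.3 percentage points. If no such event occurs, the change in incidence is zero and only outcome data are affected.

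**The case against.** The strongest reply is that the contradiction depends on how two phrases are read. If 4.4.2 concerns only subjects who leave at their own request, and the early end-of-study visit is the final visit, 7.7 applies and the related event is followed. That is a fair reading, but it is not the stated rule and it sits badly with the heading of 4.4.2. A protocol that works under one of four combinations still needs the sentence that selects it.

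The safeguards also count. Assessment is requested before exit, the early-withdrawal visit includes adverse event assessment and serious event reporting, and 7.5 gives no end date for serious event reporting. A site might therefore report a later serious event. These points limit the loss. They do not give the event's course after exit, and 4.4.2 tells the site to collect nothing more.

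Four stronger inferences are tempting, and the documents do not support them:
- *Section 3.1.3 contradicts the 30-day follow-up.* It says "The maximum participation duration per Subject is up to 19 days", but the synopsis describes the 30 days as additional to screening and treatment. The two are consistent; at most a cross-reference is missing.
- *Adverse event incidence is undercounted.* The event that led to termination is already counted. Only a new or upgraded event after exit would be missed.
- *The share of treatment days unobserved after an early exit measures the problem.* Those days go unobserved after any early exit under 4.4.2, including one with no open related event, so they do not measure its conflict with 7.7.
- *The all-cause death listing should extend over the 30-day period.* Only subjects with open related events are followed then. Deaths would be looked for longer in the arm with more such events, which would add a bias.

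**Conclusion.** The point holds in a limited form. For a subject terminated by the investigator with a treatment-related adverse event still open, 4.4.2 and 7.7 either conflict or leave the subject without follow-up, unless 4.4.2 is confined to voluntary withdrawal and 7.7 extended to the early exit visit, neither of which is stated. Follow-up of the same event can be 0 days or up to 30. A commitment to follow up appears only in 7.7; the synopsis and SAP 3.1 are permissive.

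The consequence concerns the completeness of safety data: outcome, later severity or seriousness, and events or death up to the planned Day 6-9 date. It does not show that overall adverse event incidence is wrong, and it does not bear on the primary efficacy analysis. Its size cannot be stated because the number of such subjects is not given. The 3.3-point figure holds only for one unrecorded new or upgraded event and about 30 treated subjects per arm. The change is worth making because it is cheap and removes a rule that can cut off information on subjects taken off study for harm.

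**What to change.** Reconcile 4.4.2 with 7.7:

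1. In 4.4.2, limit the stop on data collection to subjects who withdraw consent for further data collection.
2. For subjects terminated by the investigator, continue recording adverse events, serious adverse events and vital status to the planned Day 6-9 date, by chart check or telephone call.
3. In 7.7, state that the existing follow-up applies to treatment-related events open at exit, including early exit, and bring the synopsis and SAP 3.1 into line on whether it is required or optional.

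Leave 3.1.3 as it stands, and do not extend the all-cause death listing into the 30-day period.

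The change concerns recording only and says nothing about how any subject is treated. It does add something the protocol does not now provide: safety and vital status recording after termination. The cost is a wording amendment and a chart check or call for the few subjects terminated early, with no extra visit or procedure.

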## 4.5. Demographics and Subject Characteristics

The following demographic data and Subject characteristics will be collected and documented after the Subject or legally authorized representative signs the informed consent and before treatment application:

- Subject characteristics
- Comorbidities
- Wound history and characteristics

#### **4.6. Medical and Surgical History**

As part of screening procedures, the Investigator or a medically licensed sub-investigator, or a practitioner working under the licensure of the Investigator or sub-investigator, will collect a complete medical and surgical history for each Subject. If the screening visit and randomization occur on different days, the medical and surgical history will be updated (if changes have occurred) at the randomization visit prior to treatment application.

#### **4.7. Laboratory Assessment for Pregnancy**

Serum or urine assessment for human chorionic gonadotropin (hCG) to determine pregnancy status in female Subjects of child-bearing potential will be conducted during screening. If the Subject's pregnancy test is positive, she will not be eligible for randomization, will discontinue from the study, and will be considered a screen failure.

#### **4.8. Randomization and Subject Numbering**

Consented Subjects will be assigned a unique Subject identifier. Study data will be reported according to this unique Subject identifier.

Subjects who satisfy all inclusion criteria and none of the exclusion criteria will be eligible for randomization. Randomization to study treatment will be centralized, electronic, and web-based.

If a screened Subject does not meet all inclusion criteria or meets any exclusion criteria, the Subject will not be randomized and will be considered a screen failure.

#### **4.9. Wound Assessments**

Wound assessments will be performed by the Investigator or a medically licensed sub-investigator, or a practitioner working under the licensure of the Investigator or sub-investigator, according to the schedule of visits in order to capture key features of study

wounds (such as odor). A measurement of the study wound will be performed only to determine Subject eligibility.

#### **4.10. Bedside Eschar Debridement**

Bedside sharp and/or mechanical debridement procedures will be allowed before randomization to remove eschar. However, sharp or mechanical debridement of the study wound after randomization is not permitted. For those Subjects having bedside sharp and/or mechanical debridement prior to randomization, there will be two wound assessments prior to initiation of treatment.

- 1) Prior to debridement, the investigator or a medically licensed sub-investigator, or a practitioner working under the licensure of the Investigator or sub-investigator, will measure the wound to confirm that the wound size matches inclusion criteria #4 in Section 4.2.1. In addition, a three-dimensional (3D) image of the wound will be taken prior to debridement.
- 2) After debridement, the investigator will assess the wound to confirm the wound has no more than 2/3 viable tissue. In addition, a 3D image of the wound will be taken after debridement. This 3D image will be used for the baseline measurement that subsequent images are compared to for any changes in size/tissue composition.

#### **4.11. Initial Application of Study Treatments**

##### **4.11.1. V.A.C. VERAFLTM CLEANSE CHOICE™ Dressing**

For Subjects randomized to the Treatment arm, VFCC will be placed in the wound according to the manufacturer's instructions (safety information and application instructions are provided with the study products). The dressing will be covered with semi-occlusive V.A.C.® Advanced Drape with a quarter-sized hole cut in the drape for the V.A.C. VERAT.R.A.C.™ Pad. The pad should be placed directly over the hole. The normal saline solution will be connected to the system. The pre-programmed therapy unit will then be set to V.A.C. VERAFL™ Therapy and initiated to deliver a volume determined by the physician along with a 10-minute soak time followed by 3.5 hours of

V.A.C.® Therapy with a pressure of -125 mmHg. During the unit's initial drawdown, the Investigator will evaluate that there is no indication of a system leak using the Seal Check tool. The Investigator or a medically licensed sub-investigator, or a practitioner working under the licensure of the Investigator or sub-investigator, will document therapy unit settings (dwell time, pressure, and cycle time), that the system is operational, and that application of the assigned therapy is successful. Additional V.A.C.® Advanced Drape can be applied to the dressing if needed to assist in mitigating leaks.

The Fill Assist feature on the pump allows the user to monitor initial wound fill by manually starting and stopping instillation to determine correct instill volume after the dressing is applied. The Fill Assist procedure will be performed twice each time a new dressing is placed in the wound. The first time the Fill Assist is performed, the dressing is completely saturated to assist in filling or priming the dressing with a solution and purging the air in the foam. The second Fill Assist procedure is done to determine the appropriate volume to be instilled during therapy. The volume determined from the second Fill Assist procedure will be recorded.

Dressing changes are addressed in Section 4.12. Treatment removal is addressed in Section 4.13.

#### **4.11.2. Collagenase Ointment**

For Subjects randomized to the Control arm, the collagenase ointment will be placed in the wound according to the manufacturer's instructions (application instructions are provided with the study products). The approximate therapy amount (such as the total number of tubes used) will be documented. The wound will be covered with a compatible standard dressing, and dressing materials will be documented.

Dressing changes are addressed in Section 4.12. Treatment removal is addressed in Section 4.13.

#### **4.12. Dressing Changes**

The date, start time, and end time of each dressing change for both treatment groups (see Sections 4.12.1 and 4.12.2 below) will be documented by the Investigator or a

medically licensed sub-investigator, or a practitioner working under the licensure of the Investigator or sub-investigator.

#### **4.12.1. V.A.C. VERAFL0 CLEANSE CHOICE™ Dressing**

Dressing changes and treatment application can occur at the bedside. Therapy application instructions are provided with the study products. Dressing change frequency will follow the study schedule of visits (refer to Section 5.1). Dressing changes should not occur more frequently than 48 hours from the previous dressing change unless a replacement is required to maintain therapy. At each dressing change, the Investigator or a medically licensed sub-investigator, or a practitioner working under the licensure of the Investigator or sub-investigator, will document therapy unit settings (dwell time, pressure, and cycle time), that the system is operational, and that application of the assigned therapy is successful for all dressing changes.

#### **4.12.2. Collagenase Ointment**

Dressing changes and treatment application can occur at the bedside. Therapy application and dressing changes should be made following the instructions available in the package insert of the product. Dressing changes can occur daily for patients randomized to the collagenase ointment group (or more frequently if dressings become soiled). The approximate therapy amount (such as the total number of tubes used) will be documented for all dressing changes. The wound will be covered with a compatible standard dressing, and dressing materials will be documented for all dressing changes.

### **4.13. Treatment Removal**

#### **4.13.1. V.A.C. VERAFL0 CLEANSE CHOICE™ Dressing**

Subjects will remain hospitalized and on Study Treatment therapy for two (2) dressing changes (ie, 6 to 9 days). Dressing removal should not occur prior to 48 hours from the previous dressing change unless a replacement is required to maintain therapy. The Investigator may then use their wound treatment of preference to ensure the continuation of wound care. The date and time of dressing removal will be documented.

#### **4.13.2. Collagenase Ointment**

Subjects will remain on Study Treatment therapy for six (6) to nine (9) days. The Investigator may then use their wound treatment of preference to ensure the continuation of wound care. The date and time of dressing removal will be documented.

#### **4.14. 3D Imaging**

Three-dimensional wound images will be captured for each study visit using a specialized imaging system. Imaging guidelines, equipment, and supplies will be provided to the investigational sites by KCI®.

The 3D images collected from each site will be aggregated into a single database. The aggregated images will be analyzed/measured by the independent assessor. The independent assessor will determine and plot the wound perimeter, the clean, healthy, viable tissue, and other tissue types for each image. The imaging software will be used to calculate wound length, width, surface area, and wound volume. The values of these parameters/assessments will be used for calculations of the primary endpoint as described in section 8.1.1 and the secondary endpoints described in sections 8.1.2.1 and section 8.1.2.2. The 3D wound images should not be used to guide patient treatment.

